8.0 Study Procedures

8.1 Patient Screening (Visit #1)

A qualified member of the Investigator’s team will meet with the potential subject and review the patient’s medical history to screen for study eligibility. Prior to performing any screening procedures, the patient must sign the Informed Consent Form.

Clinical Assessment:

A complete history will be documented on the Demographic / Physical History CRF. Data collected will include but not be limited to:

- Date of birth, gender, ethnicity, race, height, weight
- History of concurrent or previous medical illness
- History of previous treatment received to the index hip

Evaluation Assessment by either the ***Injecting*** or ***Blinded*** Investigator (see section 12.1.1): A complete evaluation will be documented on the Screening CRF. Data collection and procedures will include:

- General medical exam
- Work status

Each subject will assess their current level of pain during walking using the Numerical Rating Scale (NRS). If the patient reports a walking pain score ≥ 4 and ≤ 8 , they may be eligible for the study.

8.2 X-ray Imaging

Patients that meet all non-radiographic inclusion/exclusion criteria must have X-rays to determine the severity of osteoarthritis in the target hip. Weight bearing, anterior-posterior (A-P) pelvic images of the hip will be acquired according to an image acquisition protocol (IAP) and transferred to a third-party imaging vendor using an image transfer protocol (ITP). Alternatively, A-P X-rays collected within 6 months prior to patient screening may be submitted using the ITP. The imaging vendor will provide a Kellgren-Lawrence (K/L) score for the patient. The K/L score will be entered in the X-Ray CRF. If all imaging criteria are met, they will be eligible to participate in the trial.

8.3 Washout Periods / Medications

Subjects will be advised that the only pain medication that they are allowed to take during this study will be acetaminophen (e.g. Tylenol), with doses not to exceed 4,000 mg/day. This should be considered rescue pain medication, and should be taken only as needed.

All subjects will be asked to refrain from taking any pain medication, except for rescue medication, for 7 days (washout period) prior to their first injection, and no pain medication of any kind should be taken for 48 hours prior to the first injection. These washout periods allow for adequate baseline pain evaluation. Subjects will be asked to keep a Medication Diary beginning after their first injection, and for the duration of their follow-up visits.

All subjects will be asked to refrain from taking any pain medication for 48 hours preceding each clinical follow-up visit to allow for adequate pain evaluation (wash-out).

8.4 Patient Compensation

Funding will be made available for patient stipends to help defray transportation and other costs associated with the follow-up visits (e.g. mileage, parking, public transportation). A maximum of \$50 per visit will be allowable for each visit.

8.5 Baseline / Randomization / Injection #1 (Day 0, Visit #2)

Baseline assessment, patient randomization and Injection #1 must be performed within 30 days of the screening visit, and should be performed on the same day

The following will be performed after the subject has signed the EC/IRB approved Informed Consent form:

A review and reconfirmation of the Inclusion/Exclusion criteria obtained at the initial screening visit will be completed by a designated member of the study team. Confirmation that subject has complied with the washout period for all pain medications for a period of at least 7 days, and 48 hours for acetaminophen, will be documented. In addition, if subject is a female of childbearing potential, she must have a negative pregnancy test, or document her inability to become pregnant (e.g. surgically sterile). Confirmation of K-L grade 2/3 hip OA should be performed before the baseline visit. Subjects who maintain study qualification will be randomized to receive either MONOVISC or Saline.

Evaluation Assessment by either the ***Injecting*** or ***Blinded*** Investigator (see section 12.1.1): A complete evaluation will be documented on the Screening CRF. Data collection and procedures will include:

- General medical exam
- Work status
- Current medication consumption

Each subject will then complete the following self-report questionnaires:

- Western Ontario MacMaster (WOMAC)
- Patient Global Assessment (PGA)
- SF-12

8.5.1 Randomization & Injection

Prior to the start of the study, a computer generated random list of treatment assignments (Master Randomization List) will be created using a 2:1 schema to either MONOVISC or saline injection, and patient kits of MONOVISC and saline will be sequentially numbered according to this list. Investigational sites will be provided with an initial, sequentially numbered quantity of kits to be used, and as these kits are utilized, additional quantities of sequentially numbered kits can be ordered by the site. With this randomization scheme, each study subject will be associated with a unique kit number, and the order of randomized subjects at each investigational site will be distinct. The syringe contents will be physically blinded. However, due to the difference in syringe plunger pressure required to eject MONOVISC compared to saline, the Investigator performing the injections will likely know whether they are injecting MONOVISC or saline. As such, a designated Injecting Investigator will be responsible for the injection of either MONOVISC or saline. Non-injecting Blinded Investigators will perform all follow-up evaluations to ensure that blinding is maintained. However, Injecting Investigators may participate in screening and pre-injection baseline evaluations.

Final enrollment anticipated:

- 374 subjects receiving two 4-mL injections of MONOVISC, separated by 1 month (active treatment)

- 186 subjects receiving two 4-mL injections of saline, separated by 1 month (control)

All clinical research and biostatistics personnel at DePuy Synthes Mitek Sports Medicine will remain blinded to treatment assignment until the end of the study. An employee within Strategic Medical Affairs will be designated to maintain the Master Randomization, to facilitate any medical safety reviews, if necessary, and to facilitate the planned interim futility analysis. This individual will be authorized to unblind a site for any patient in the event of an Adverse Event that requires treatment.

The Injecting Investigator will obtain the next sequentially numbered patient kit from the secure storage area. The kit will not contain any labeling to indicate whether the patient is receiving MONOVISC or Saline. If the Investigator discovers the presence of a condition at the time of injection that would render the subject ineligible for study participation, the subject should not be injected and will be considered a screen fail; the patient kit will be returned to the storage area to be used with the next study subject. The ineligible subject should then receive the standard of care as determined by the enrolling Investigator. The reason for subject ineligibility will be documented on the Screening and Enrollment Log.

Prior to injection, sterile drapes or other suitable means should be used to block the patient's view of the injection and the imaging monitor. Under fluoroscopic or ultrasound guidance, the patient will receive an intra-articular hip injection of either MONOVISC or saline. Injection technique should follow established procedures for IA hip injection, such as those used for injections of corticosteroid or imaging contrast agents. Details of a typical image-guided injection procedure are described in Appendix C.

During intra-articular hip injections, it is common to use extension tubing to connect the syringe to the needle. However, due to the high viscosity of MONOVISC, it can be very difficult to inject the solution through such tubing. Moreover, some of the injected liquid can remain in the tubing rather than being injected into the joint. For these reasons, extension tubing should not be used for the intra-articular injections in this study.

The Injecting Investigator will evaluate and report any Adverse Events that occur as part of the injection procedure.

Identical post-injection instructions will be given to all subjects, regardless of randomization. Patients will be advised to refrain from rigorous physical activity for 48 hours post-injection. All subjects will be permitted to take acetaminophen (e.g. Tylenol) only (through the 26 week follow-up visit) if necessary, for the control of injection site pain or for general joint pain, at a maximum rate of 4000 mg in a 24 hour period. Acetaminophen use will be monitored at each subsequent follow-up visit as self-reported by the subject (Sec. 8.3)

8.6 Follow-Up Visits – No injections (Visits 3, 5, 6 & 7)

Post-injection follow-up visits, with no injections, will occur on Days 14 ± 3 , 60 ± 14 , 120 ± 14 , and 180 ± 21 (Visits 3, 5, 6 and 7). At each visit, each subject will complete the following self-report questionnaires:

- Western Ontario MacMaster (WOMAC)
- Patient Global Assessment (PGA)
- SF-12

The patient will also submit their completed patient diary for evaluation.

Evaluation Assessment by ***Blinded Investigator only:***

A complete evaluation will be documented on the follow-up CRFs. Data collection and procedures will include:

- Work status
- History of concurrent or previous medical illness
- Medication review
- Adverse events / secondary procedures

8.7 Injection #2 (Day 28 ± 7, Visit #4)

Prior to the second injection of MONOVISC or saline, each subject will complete the following self-report questionnaires:

- Western Ontario MacMaster (WOMAC)
- Patient Global Assessment (PGA)
- SF-12

The patient will also submit their completed patient diary for evaluation.

Evaluation Assessment by ***Blinded Investigator only:***

A complete evaluation will be documented on the Follow-up CRF. Data collection and procedures will include:

- Work status
- History of concurrent or previous medical illness
- Medication review
- Adverse events / secondary procedures

After completion of questionnaires and evaluation assessment, the patient will receive the 2nd injection of either MONOVISC or saline from the same product kit that was utilized for the 1st injection, using procedures employed for the first injection. The injection must be performed by an *Injecting Investigator*. The Injecting Investigator will also evaluate and report any Adverse Events that occur as part of the injection procedure.

8.8 Unscheduled Visit Procedures

If an unscheduled visit falls between the injection procedure and Week 26, the evaluation assessment must be performed by a ***Blinded*** Investigator. Evaluation assessment should not be performed if the unscheduled visit is deemed unrelated to the study treatment, or is considered a Standard of Care visit.

The patient will also submit their completed patient diary for evaluation.

Evaluation Assessment by ***Blinded Investigator only:***

A complete evaluation will be documented on the Follow-up CRF. Data collection and procedures will include:

- Work status
- History of concurrent or previous medical illness
- Medication review
- Adverse events / secondary procedures

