9.0 ADVERSE EVENT REPORTING

9.1 Anticipated Adverse Events

These are immediate post-injection or peri-injection events that are changes from the baseline condition of the Subject, but are expected events resulting from the treatment. If these events occur, they should be recorded in the Subject's medical record.

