9.2 Adverse Events

An Adverse Event is any untoward medical occurrence in a subject, regardless if there is a relationship between the adverse events and the study devices.

At each evaluation of the subject enrolled in a clinical investigation, the Investigator determines whether any adverse events (AE) have occurred, and determines their relationship to the study devices or procedure.

All adverse events, study device malfunctions and other product issues must be recorded in the medical records and entered into electronic Case Report Forms (eCRFs) within two weeks of awareness the AE occurred. Upon entry of an AE into the eCRF, designated members of the DePuy Synthes Mitek clinical team will receive an email alert describing the AE.

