As MONOVISC is an approved device for the treatment of OA in the knee, certain AE are known to be associated with single intra-articular knee injections of MONOVISC. These can be found in the MONOVISC Package Insert⁴. These events are expected to be similar for hip injections; however, risks may be elevated in the present study since the protocol calls for two injections of MONOVISC rather than one injection. In the clinical trial for MONOVISC, adverse events that were related to the injection treatment were the following and are considered Anticipated AE:

- injection site pain/swelling;
- joint stiffness / swelling / effusion;
- arthralgia, or aggravated osteoarthritis;
- pain in extremity;
- synovitis;

- contusion;
- subcutaneous nodule;
- Baker's cyst.

AE will be summarized as followings with the number of events and the number and proportion of subjects with events. This analysis will be conducted using the Safety Analysis Set:

- All AE;
- All Device or Procedure Related AE (defined as possible, probable, or related);
- All AE leading to treatment discontinuation;
- All AE by Severity;
- All AE by Relationship (to investigational products or any protocol mandated procedures);
- All SAE;
- All UADE;
- All Anticipated AE.

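### Protocol 8.8 and 9.1 are worded inconsistently with 9.2, 9.6 and schedule 1.1, and could lead sites to under-record unrelated or expected adverse events

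*Protocol*

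**What the plan says.** **Unscheduled visits.** Protocol 8.8 requires a Blinded Investigator to perform the evaluation assessment at an unscheduled visit between injection and Week 26. It then says: "Evaluation assessment should not be performed if the unscheduled visit is deemed unrelated to the study treatment, or is considered a Standard of Care visit". Elsewhere in 8.8 the contents of the assessment are listed, documented on the Follow-up CRF: work status, illness history, medication review, and "Adverse events / secondary procedures".

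**Expected events.** Protocol 9.1 describes immediate post-injection or peri-injection events that are expected from the treatment. Its only recording instruction is: "If these events occur, they should be recorded in the Subject's medical record".

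**The general rule.** Protocol 9.2 defines an AE as "any untoward medical occurrence in a subject, regardless if there is a relationship between the adverse events and the study devices". It has the Investigator determine AEs and their relationship at each evaluation. It also says that all AEs "must be recorded in the medical records and entered into electronic Case Report Forms (eCRFs", within two weeks of awareness. Protocol 9.6 runs AE reporting from the start of the injection procedure to the end of participation, and its causality scale includes Unrelated.

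**The schedule.** The AE / secondary procedures row of Protocol 1.1 is marked in the unscheduled-visit column. Its footnote concerns who evaluates, not whether the event looks related.

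**The SAP.** SAP 13.5.1 puts the all-AEs-into-CRFs rule and the medical-record sentence for expected events in one paragraph without reconciling them, then lists "All Anticipated AE" among its summaries. SAP 9.4 makes AE incidence, MONOVISC against saline through 26 weeks and including events during injection, the safety assessment. SAP 13 plans Fisher's exact test for AE rates.

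**The concern.** The order of steps in 8.8 is the main problem. Relatedness is supposed to be an output of AE assessment, rated on the 9.6 scale. In 8.8 it becomes an entry condition: if someone has already deemed the visit unrelated, the step that would identify and rate the event is not done. The section does not say who makes that decision. The standard-of-care exemption has a similar effect, since a routine visit for the target hip is a natural place for a secondary procedure to come to light.

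The problem in 9.1 is one of destination. It names one place for expected events and the next section names two. A site could reasonably read the specific instruction as an exception to the general one, and sites may read it differently.

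At stake is the completeness of the between-arm AE comparison, chiefly for non-serious events presenting between visits and for expected peri-injection events, which the endpoint explicitly includes. There is a smaller knock-on: medication and secondary-procedure information can bear on protocol violations, and SAP 14.2 says that safety data are needed to decide membership of the interim Per Protocol set. The pain scores for the primary endpoint are not affected.

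**Working it through.** No figure in the plan is at stake, so the check is a reconciliation of text, followed by the visit-gap arithmetic and a labelled illustration.

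**1. 8.8 against the other rules**
- AE collected at an unscheduled visit? Schedule 1.1: yes, without condition. Protocol 8.8: not if the visit is deemed unrelated or standard of care. These conflict.
- Does relatedness limit what counts as an AE? Protocol 9.2: no. Protocol 9.6: no, because Unrelated is a rating for a reported event. Protocol 8.8 applies relatedness before the evaluation at which 9.2 has AEs determined.
- Is an event learned of at an exempt visit barred from the CRF? No. The 9.2 entry duty runs from awareness and still applies. What 8.8 removes is the prompt to look.

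**2. 9.1 against the other rules**
- Destination in 9.1: medical record; silent on the eCRF. Destination in 9.2: medical record and eCRF.
- Protocol 8.5.1 and 8.7 have the Injecting Investigator evaluate and report any AE of the injection procedure, which points to capture.
- The SAP summary of anticipated AEs needs these events in the database, so the intent is evidently to collect them. The wording of 9.1 does not say so.

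**3. Time to the next scheduled AE review** (windows from Protocol 11.4)
- Visit 5 (days 46 to 74) to Visit 6 (days 105 to 134): longest gap 134 − 46 = 88 days.
- Visit 6 to Visit 7 (days 159 to 201): longest gap 201 − 105 = 96 days. With the ±14 days of schedule 1.1, the earliest Visit 6 is 120 − 14 = day 106, giving 95.
- Nominal gaps: 120 − 60 = 60 and 180 − 120 = 60 days. The longer figures need the earliest possible visit followed by the latest possible one.
- A patient who withdraws before the next visit may have no later scheduled review.

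**4. Illustration only.** The documents give no AE rates or capture fractions; those below are assumptions. Let a fraction c of affected subjects be captured equally in both arms, so observed incidence is c × true incidence. Take n0 = 186 saline and n1 = 2 × 186 = 372 MONOVISC (the plan has 374). Normal approximation, not Fisher's exact test:

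Power = Φ[(d − 1.96·SE0)/SE1], with d = c(p1 − p0), SE0 = √[p̄(1 − p̄)(1/n0 + 1/n1)], SE1 = √[q0(1 − q0)/n0 + q1(1 − q1)/n1], where q0 = c·p0, q1 = c·p1 and p̄ = (q0 + 2·q1)/3.

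For 20% saline against 30% MONOVISC at c = 1: p̄ = 0.2667, SE0 = 0.0397, SE1 = 0.0377, and (0.10 − 0.0778)/0.0377 = 0.587, so power is 0.72.

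| True incidence, saline vs MONOVISC | c = 100% | 90% | 75% | 50% |
|---|---|---|---|---|
| 10% vs 20% | 0.87 | 0.83 | 0.74 | 0.52 |
| 20% vs 30% | 0.72 | 0.66 | 0.55 | 0.37 |
| 40% vs 50% | 0.61 | 0.53 | 0.42 | 0.25 |
| Observed difference (points) | 10.0 | 9.0 | 7.5 | 5.0 |

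Equal loss shrinks a real difference towards zero. If capture differed by arm with no true difference, say 20% incidence with 75% captured on MONOVISC and 90% on saline, the observed difference would be 0.20 × 0.75 − 0.20 × 0.90 = 0.15 − 0.18 = −3 points. Nothing in the documents says which pattern, if either, would arise.

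**The case against.** The strongest reply is that the protocol already requires these events to be entered. The 9.2 duty covers all AEs and is triggered by awareness, not by a completed assessment. Protocol 9.3 requires any serious AE within 72 hours with no relatedness filter. Protocol 9.6 sends AEs to the Adverse Events CRF. Protocol 8.5.1 and 8.7 require injection-procedure AEs to be reported, and Protocol 8.6 and 8.7 collect AEs, illness history and medications at Visits 3 to 7. Under 12.8 monitors cross-check CRFs with source documents. Read with 9.2, 9.1 is merely incomplete.

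Most of that stands, and it rules out two stronger readings that a reader might infer. The first is that 8.8 and 9.1 keep AEs out of the CRF, making the comparison incomplete by rule. Neither section prohibits entry: 8.8 limits a visit procedure, and 9.1 does not restrict recording to the medical record.

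The second is that the loss would differ by arm. Follow-up assessors and the coordinator are blinded, and 12.1.2 bars the Injecting Investigator from follow-up data collection. AEs at the injections are evaluated by that unblinded investigator, so a route exists for the events 9.1 covers, but a route is not evidence of bias.

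What the reply does not remove is the direct conflict between 8.8 and schedule 1.1. Nor can a duty triggered by awareness replace an assessment whose purpose is to create awareness.

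**Conclusion.** The inconsistency is real and should be corrected. Protocol 8.8 withholds AE, secondary-procedure and medication review on a prior relatedness or standard-of-care judgement by an unnamed person, against 1.1, 9.2 and 9.6. Protocol 9.1 and its SAP counterpart leave the eCRF unmentioned for expected peri-injection events, against 9.2 and the SAP's own planned summary. The consequence is a risk that sites under-record unrelated or expected, mainly non-serious, AEs.

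The size of that risk cannot be derived: the documents give neither the frequency of exempt visits nor AE rates, and do not show how sites read 9.1. The gaps of 88 and 96 days are the longest the windows allow, and the power figures rest wholly on assumed incidences and capture fractions. The documents support neither certain loss of events nor a biased arm comparison.

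**What to change.** **Protocol 8.8.** Remove adverse events / secondary procedures and medication review from the exemption. State that they are recorded on the CRF at every unscheduled visit the site learns of, whatever its presumed cause, with relatedness rated afterwards by the Blinded Investigator. The exemption may remain for work status, illness history and the questionnaires. The questionnaires should be named explicitly, because schedule 1.1 lists them for unscheduled visits but 8.8 does not.

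**Protocol 9.1 and the matching SAP 13.5.1 sentence.** State that anticipated events are also entered in the AE eCRF as in 9.2. The protocol edit is the one that changes what sites collect; the SAP edit keeps the documents aligned.

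**Cost.** Changes to a few sentences and a memo to sites. Expect somewhat more minor AE entry and a slightly higher reported AE rate in both arms. It is best done early, since events never recorded may not be recoverable at database lock.

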8.9 Study Period

Enrollment for the study is anticipated to require approximately 30 months (up to 560 patients). Each patient's participation will be at least 26 weeks from the time of the initial injection until their final follow up visit. Therefore, the estimated total duration for the study will be approximately 36 months.

9.0 ADVERSE EVENT REPORTING

9.1 Anticipated Adverse Events

These are immediate post-injection or peri-injection events that are changes from the baseline condition of the Subject, but are expected events resulting from the treatment. If these events occur, they should be recorded in the Subject's medical record.

